7.1.3. Cabozantinib Special warnings and precautions for use

1) Hepatic effects

Abnormalities of liver function tests (increases in alanine aminotransferase [ALT], aspartate aminotransferase [AST] and bilirubin) have been frequently observed in patients treated with cabozantinib. It is recommended to perform liver function tests (ALT, AST and bilirubin) before initiation of cabozantinib treatment and to monitor closely during treatment. For patients with worsening of liver function tests

considered related to cabozantinib treatment (i.e. where no alternative cause is evident), the dose modification advice in section 7.1.2). Cabozantinib is eliminated mainly via the hepatic route. Closer monitoring of the overall safety is recommended in patients with mild or moderate hepatic impairment (see also section 7.1.2). A higher relative proportion of patients with moderate hepatic impairment (Child-Pugh B) developed 6 hepatic encephalopathy with cabozantinib treatment. Cabozantinib is not recommended for use in patients with severe hepatic impairment (Child-Pugh C) as cabozantinib has not been studied in this population and exposure might be increased in these patients.

2) Hepatic encephalopathy

In the HCC study (CELESTIAL), hepatic encephalopathy was reported more frequently in the cabozantinib than the placebo arm. Cabozantinib has been associated with diarrhoea, vomiting, decreased appetite and electrolyte abnormalities. In HCC patients with compromised livers, these non-hepatic effects may be precipitating factors for the development of hepatic encephalopathy. Patients should be monitored for signs and symptoms of hepatic encephalopathy.

3) Perforations and Fistulas

Fistulas, including fatal cases, occurred in 1% of cabozantinib-treated patients. Gastrointestinal (GI) perforations, including fatal cases, occurred in 1% of cabozantinib-treated patients.

Monitor patients for signs and symptoms of fistulas and perforations, including abscess and sepsis. Discontinue cabozantinib in patients who experience a fistula which cannot be appropriately managed or a GI perforation.

4) Gastrointestinal (GI) disorders

Diarrhoea, nausea/vomiting, decreased appetite, and stomatitis/oral pain were some of the most commonly reported GI adverse reactions. Prompt medical management, including supportive care with antiemetics, antidiarrheals, or antacids, should be instituted to prevent dehydration, electrolyte imbalances and weight loss. Dose interruption or reduction, or permanent discontinuation of cabozantinib should be considered in case of persistent or recurrent significant GI adverse reactions.

Diarrhea occurred in 63% of patients treated with cabozantinib. Grade 3 diarrhea occurred in 11% of patients treated with cabozantinib.

Withhold cabozantinib until improvement to Grade 1 and resume cabozantinib at a reduced dose for intolerable Grade 2 diarrhea, Grade 3 diarrhea that cannot be managed with standard anti diarrhea treatments, or Grade 4 diarrhea.

5) Thrombotic Events

Cabozantinib increased the risk of thrombotic events. Venous thromboembolism occurred in 7% (including 4% pulmonary embolism) and arterial thromboembolism occurred in 2% of cabozantinib-treated patients. Fatal thrombotic events occurred in cabozantinib-treated patients.

Discontinue cabozantinib in patients who develop an acute myocardial infarction or serious arterial or venous thromboembolic events that require medical intervention

6) Hemorrhage

Severe and fatal hemorrhages occurred with cabozantinib. The incidence of Grade 3 to 5 hemorrhagic events was 5% in cabozantinib-treated patients. Discontinue cabozantinib for Grade 3 or 4 hemorrhage. Do not administer cabozantinib to patients who have a recent history of hemorrhage, including hemoptysis, hematemesis, or melena.

7) Thrombocytopenia

In the HCC study (CELESTIAL), thrombocytopenia and decreased platelets were reported. Platelet levels should be monitored during cabozantinib treatment and the dose modified according to the severity of the thrombocytopenia (see section 7.1.2).

8) Wound Complications

Wound complications have been reported with cabozantinib. Stop cabozantinib at least 28 days prior to scheduled surgery. Resume cabozantinib after surgery based on clinical judgment of adequate wound healing. Withhold cabozantinib in patients with dehiscence or wound healing complications requiring medical intervention.

9) Hypertension and Hypertensive Crisis

Cabozantinib can cause hypertension, including hypertensive crisis. Hypertension was reported in 36% (17% Grade 3 and <1% Grade 4) of cabozantinib treated patients.

Do not initiate cabozantinib in patients with uncontrolled hypertension. Monitor blood pressure regularly during cabozantinib treatment. Withhold cabozantinib for hypertension that is not adequately controlled with medical management; when controlled, resume cabozantinib at a reduced dose. Discontinue cabozantinib for severe hypertension that cannot be controlled with antihypertensive therapy or for hypertensive crisis.

10) Palmar-Plantar Erythrodysesthesia

Palmar-plantar erythrodysesthesia (PPE) occurred in 44% of patients treated with cabozantinib. Grade 3 PPE occurred in 13% of patients treated with cabozantinib.

Withhold cabozantinib until improvement to Grade 1 and resume cabozantinib at a reduced dose for intolerable Grade 2 PPE or Grade 3 PPE.

11) Proteinuria

Proteinuria was observed in 7% of patients receiving cabozantinib. Monitor urine protein regularly during cabozantinib treatment. Discontinue cabozantinib in patients who develop nephrotic syndrome.

12) Reversible Posterior Leukoencephalopathy Syndrome

Reversible Posterior Leukoencephalopathy Syndrome (RPLS), a syndrome of subcortical vasogenic edema diagnosed by characteristic finding on MRI, can occur with cabozantinib. Perform an evaluation for RPLS in any patient presenting with seizures, headache, visual disturbances, confusion or altered mental function. Discontinue cabozantinib in patients who develop RPLS.

13) Prolongation of QT interval

Cabozantinib should be used with caution in patients with a history of QT interval prolongation, patients who are taking antiarrhythmics, or patients with relevant pre-existing cardiac disease, bradycardia, or electrolyte disturbances. When using cabozantinib, periodic monitoring with on-treatment ECGs and electrolytes (serum calcium, potassium, and magnesium) should be considered.

14) Biochemical laboratory test abnormalities

Cabozantinib has been associated with an increased incidence of electrolyte abnormalities (including hypo- and hyperkalemia, hypomagnesaemia, hypocalcaemia, hyponatremia). It is recommended to monitor biochemical parameters during cabozantinib treatment and to institute appropriate replacement therapy according to standard clinical practice if required. Cases of hepatic encephalopathy in HCC patients can be

attributed to the development of electrolyte disturbances. Dose interruption or reduction, or permanent discontinuation of cabozantinib should be considered in case of persistent or recurrent significant abnormalities (see section 7.1.2).

15) Osteonecrosis of the Jaw

Osteonecrosis of the jaw (ONJ) occurred in <1% of patients treated with cabozantinib. ONJ can manifest as jaw pain, osteomyelitis, osteitis, bone erosion, tooth or periodontal infection, toothache, gingival ulceration or erosion, persistent jaw pain or slow healing of the mouth or jaw after dental surgery. Perform an oral examination prior to initiation of cabozantinib and periodically during cabozantinib. Advise patients regarding good oral hygiene practices. Withhold cabozantinib for at least 28 days prior to scheduled dental surgery or invasive dental procedures, if possible. Withhold cabozantinib for development of ONJ until complete resolution.

16) Embryo-Fetal Toxicity

Based on data from animal studies and its mechanism of action, cabozantinib can cause fetal harm when administered to a pregnant woman. Cabozantinib administration to pregnant animals during organogenesis resulted in embryolethality at exposures below those occurring clinically at the recommended dose, and in increased incidences of skeletal variations in rats and visceral variations and malformations in rabbits.

Advise pregnant women of the potential risk to a fetus. Advise females of reproductive potential to use effective contraception during treatment with cabozantinib and for 4 months after the last dose.

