7.1.2. Dose modifications

The allowed dosing schemes of this trial are:

- *Level 0 (starting dose): cabozantinib 40 mg qd + atezolizumab 1200 mg iv every 21 days (one cycle)*
- *Level -1: cabozantinib 20 mg qd + atezolizumab 1200 mg iv every 21 days (one cycle)*

If cabozantinib is temporarily or definitively interrupted for its toxicity, atezolizumab will be continued, unless the toxicity of cabozantinib prevents the administration of atezolizumab or increases the risk of atezolizumab toxicity. In this case, both treatments will be interrupted until toxicity resolution (or NCI CTCAE grade 1) or definitively.

If one of the two drugs is discontinued or interrupted due to toxicity, the administration of the other drug should continue according to the protocol schedule.

All dose reductions and interruptions (including any missed doses), and the reasons for the reductions/interruptions are to be recorded in the eCRF and patient record.

As previously mentioned, cabozantinib dose reduction to 20 mg qd is allowed. Once reduced, dose re-escalation of cabozantinib is allowed in the opinion of the Principal Investigator, taking into account clinical benefit, type and degree of toxicity that produced the dose reduction.

Cabozantinib should be withheld for:

- Intolerable Grade 2 adverse reactions
- Grade 3 or 4 adverse reactions
- Osteonecrosis of the jaw

Upon resolution/improvement (i.e., return to baseline or resolution to Grade 1) of an adverse reaction, reduce the dose as follows:

- If previously receiving 40 mg daily dose, resume treatment at 20 mg daily.
- If previously receiving 20 mg daily dose, resume at 20 mg if tolerated, otherwise, discontinue cabozantinib.

Permanently discontinue cabozantinib for any of the following:

- Severe hemorrhage
- Development of gastrointestinal (GI) perforation or unmanageable fistula
- Serious thromboembolic event (e.g., myocardial infarction, cerebral infarction)
- Hypertensive crisis or severe hypertension despite optimal medical management
- Nephrotic syndrome
- Reversible posterior leukoencephalopathy syndrome

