8. STUDY ASSESSMENTS

8.1. SCHEDULE FOR TESTS AND DETERMINATIONS

Study assessments should be performed following the indications of this schedule of determinations and when clinically indicated according treating clinician (i.e: more frequent determinations in case of toxicities).

Table 2. Schedule for test and determinations throughout the study period

	Screening	C1	C2	C3	C4	C5	C6	C7 to PD	EOT	Up to EOS	
Week	-4 To -1	0	Q3w ±3 days unless dosing needs to be held for toxicity reasons				Q3w ±3 days unless dosing needs to be held for toxicity reasons				
Day	-28 To -1	1 ^a	Q21 Days ±3 days unless dosing needs to be held for toxicity reasons				Q21 Days ±3 days unless dosing needs to be held for toxicity reasons				
Informed Consent											
Informed Consent ^b	X										
Consent and Collection of Specimens for Future Biomedical Research	X										
Study Procedures											
Medical History	X										
Physical Exam (Full)	X										
Targeted Physical Exam (Based On Symptoms)		X	X	X	X	X	X	X	X		
Vital Signs ^c	X	X	X	X	X	X	X	X	X		
ECG ^d	X	As clinically indicated							X		
Prior and Concomitant Medications	<----->										
Demography, Including Baseline Characteristics And Tobacco Use	X										
Eligibility Criteria	X										
Laboratory Assessments											
Clinical Chemistry ^e	X	X ^f	X	X	X	X	X	X	X		
Hematology ^e	X	X ^f	X	X	X	X	X	X	X		
TSH ^g (Reflex Free T3 Or Free T4 ^h)	X	X	X	X	X	X	X	X	X		
Hepatitis B, C and HIV ⁱ	X										
Urinalysis	X									X	
Tumor markers ^q	X	q12w ± 2w until objective disease progression or death (whichever occurs first).									
Pregnancy Test ^j	X	If clinically indicated									
Monitoring											
ECOG Performance Status	X	X	X	X	X	X	X	X	X		
QoL (EQ-5D-5L, EORTC QLQ-C30) ^p	X		X		X		X	q6w		X	
AE/SAE/AESI Assessment ^k		X	X	X	X	X	X	X	X		
Post-treatment Follow-up ^l										X	
IMPs Administration											
Cabozantinib ^m			X (p.o. daily, until PD or unacceptable toxicity)								
Atezolizumab ^m			X (IV. q3w, 21 days ±3 days until PD or unacceptable toxicity)								
Biological samples collection											
Tumor Biopsy (Archival, If Available)	X										
Processed blood samples ⁿ	X		X							X	
Efficacy Evaluations											
Tumor evaluation (CT scan or MRI) (RECIST 1.1) ^o	X	q12w ± 2w until objective disease progression/death (whichever comes first).									

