- o) CT Scan or MRI is to be performed at baseline and q12w ± 2w until the objective disease progression or death (whichever comes first). Image assessments by CT scan or MRI may be performed q8w ± 2w if required by local standard clinical practice or by investigator criteria, as long as the frequency of assessments is maintained. The schedule of q12w ± 2 week (q8w ± 2w when applicable) must be followed regardless of any delays in dosing, in case of suspected pseudo-progression; treatment should be continued until progression of disease is confirmed from the imaging results. RECIST assessments will be performed on images from CT scans (preferred) or MRI, each preferably with IV contrast of the neck, chest, abdomen (including liver and adrenal glands), and pelvis. Pelvic imaging is recommended only when primary or metastatic disease in the pelvic region is likely. Additional anatomy should be imaged based on signs and symptoms of individual patients at baseline and follow-up. Baseline assessments should be performed no more than 28 days before the date of inclusion and, ideally, should be performed as close as possible to and prior to the start of treatment.
- p) EQ-5D-5L and EORTC QLQ-C30 Questionnaires (appendix 2 and 3) will be done prior to the start of treatment (at screening) and every 2 cycles (q6w, 42 days) thereafter until PD.
- q) Tumor markers should be analyzed at screening and every 12 weeks ± 2 weeks to determine the non-radiological response. The markers to collect are NSE in tumors from cohort 1, CGA in tumors from cohort 5, cortisol in functionant tumors from cohort 3, metanephrines and adrenaline in functionant tumors from cohort 4. Norepinephrine, 5-HIAA and CEA may be collected when considered.

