The investigator or qualified designee will review prior medication use including any protocol-specified washout requirement, and record prior medication taken by the subject within 4 weeks of first dose of the study treatment.
- *Concomitant Medications:*
 - The investigator or qualified designee will record the medication, if any, taken by the subject during the trial from the time of signing the informed consent form until the Safety Follow-up Visit.
 - All medications related to reportable SAEs should be recorded
 -

Demography, Including Baseline Characteristics And Tobacco Use

- Date of birth (month/year of birth) or age at informed consent, race, and sex.
- Smoking history: never smoke (≤ 100 cigarettes/life time), former smoker (≥ 1 year), smoker, unknown)
- Tobacco use: pack/year and cigarettes/day.

Eligibility Criteria

All inclusion and exclusion criteria will be reviewed by the investigator or qualified designee to ensure that each subject qualifies for the trial. More details on criteria for patients' eligibility are in section 6.1 and 6.2.

Laboratory Assessments

The summary of the procedures required is summarised in Table 2 and flow chart (Section 8.1 and the corresponding footnotes). Laboratory tests for screening should be performed within 7 days prior to study enrolment. If performed < 14 days prior to the first dose of trial therapy, the screening laboratory tests will serve as cycle 1 day 1 laboratory tests. If not, laboratory tests will need to be performed again on day 1 of cycle 1. Laboratory determinations include full clinical chemistry panel (including albumin, alkaline phosphatase, LDH, calcium, magnesium, phosphorus, sodium, potassium, creatinine, creatine kinase, direct bilirubin, indirect bilirubin, total bilirubin, total protein, urea, uric acid, amylase, lipase, glucose, ALT, AST, ALP, GGT), hematological counts (total white blood cell count with leukocyte formula, haemoglobin, and platelet count), TSH hormone levels, serology (HIV, HBV, and HCV), urianalysis and tumor markers (NSE in tumors from cohort 1, CGA in tumors from cohort 5, cortisol in functionant tumors from cohort 3, metanephrides and, adrenaline in functionant tumors from cohort 4. Norepinephrine, 5-HIAA and CEA may be collected when considered).

Pregnancy test

A serum pregnancy test must be performed at screening (at the local laboratory) within ≤ 72 hours before the *first dose of study treatment (if clinically indicated)*.

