8.2.2. Assessment during treatment

Physical Exam

- *Targeted Physical Exam (prior treatment administration):* Additional physical exams (targeted) should be performed based on investigator criteria as specified in the Trial Flow Chart (Section 8.1), considering the disease under study, patient symptoms, and prior physical exams. After the first dose of trial treatment, new clinically significant abnormal findings should be recorded as AEs.

Vital Signs

- The investigator or qualified designee will take vital signs as specified in the Trial Flow Chart (Section 8.1).
- Vital signs should include temperature, pulse, respiratory rate, weight, and blood pressure. Body weight is to be recorded at each visit along with vital signs; however, height will be measured at screening only.

Laboratory Assessments

The summary of the procedures required is summarised in Section 8.1 and the corresponding footnotes. It is recommended that laboratory tests be performed < 3 days prior to the next dose of trial therapy in order to have the results to decide on the continuity of study treatment (dose modifications and delays, among other relevant clinical decisions).

Laboratory determinations include full clinical chemistry panel (including albumin, alkaline phosphatase, LDH, calcium, magnesium, phosphorus, sodium, potassium, creatinine, creatine kinase, direct bilirubin, indirect bilirubin, total bilirubin, total protein, urea, uric acid, amylase, lipase, glucose, ALT, AST, ALP, GGT), hematological counts (total white blood cell count with leukocyte formula, haemoglobin, and platelet count), TSH hormone levels, and tumor markers.

Tumor markers should be analyzed at screening and every 12 weeks \pm 2 weeks until PD or death (whichever occurs first) to determine the non-radiological response. The markers to collect are NSE in tumors from cohort 1, CGA in tumors from cohort 5, cortisol in functionant tumors from cohort 3, metanephhrines and, adrenaline in functionant tumors from cohort 4. Norepinephrine, 5-HIAA and CEA may be collected when considered.

Eastern Cooperative Oncology Group (ECOG) Performance Status

The investigator or qualified designee will assess ECOG performance status **prior to the administration** of each dose of atezolizumab as specified in the Table of Schedule of Assessments (Table 2). It is **important to**

collect ECOG Status in patient's record and eCRF.

Adverse Event (AE)/Serious Adverse Events (SAE) assessment

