8.2.3. End of treatment Visit

Physical Exam

- *Targeted Physical Exam (prior treatment administration):* Additional physical exams (targeted) should be performed based on investigator criteria as specified in the Trial Flow Chart-Section 8.1, considering the disease under study, patient symptoms, and prior physical exams. After the first dose of trial treatment, new clinically significant abnormal findings should be recorded as AEs.

Vital Signs

- The investigator or qualified designee will take vital signs as specified in the Trial Flow Chart-Section 8.1.

- Vital signs should include temperature, pulse, respiratory rate, weight, and blood pressure. Body weight is to be recorded at each visit along with vital signs; however, height will be measured at screening only.

12-Lead Electrocardiogram (ECG)

A standard 12-lead ECG will be performed at baseline and at end of treatment visit using local standard procedure. Any clinically significant abnormalities detected require triplicate ECG results and should be recorded as medical history or adverse event, and monitored if needed. No new ECGs will be performed unless clinically indicated.

Laboratory Assessments

The summary of the procedures required is summarised in Section 8.1 and in the corresponding footnotes. It is recommended that laboratory tests be performed < 3 days prior to the EOT visit.

Laboratory determinations include full clinical chemistry panel (including albumin, alkaline phosphatase, LDH, calcium, magnesium, phosphorus, sodium, potassium, creatinine, creatine kinase, direct bilirubin, indirect bilirubin, total bilirubin, total protein, urea, uric acid, amylase, lipase, glucose, ALT, AST, ALP, GGT), hematological counts (total white blood cell count with leukocyte formula, haemoglobin, and platelet count), TSH hormone levels, and tumor markers (NSE in tumors from cohort 1, CGA in tumors from cohort 5, cortisol in functionant tumors from cohort 3, metanephrides and, adrenaline in functionant tumors from cohort 4. Norepinephrine, 5-HIAA and CEA may be collected when considered).

Eastern Cooperative Oncology Group (ECOG) Performance Status

The investigator or qualified designee will assess ECOG performance status. It is **important to record ECOG Status in patient's record and eCRF**.

Adverse Event (AE)/Serious Adverse Events (SAE) assessment

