10.7. STATISTICAL METHODS

Analysis will be based on observed data, and missing data for drop-outs are not replaced by methods like LOCF (last option carried forward).

Continuous data will be presented with the number of observations, mean value, standard deviation, minimum, maximum, and median. Categorical data will be presented as counts and percentages. Individual subject data will be listed.

Vital signs, ECG parameters, clinical laboratory data (haematology, serum biochemistry, and urinalysis) will be presented in tabular form. Values outside the reference range will be flagged, and the clinically significantly abnormal values will be listed in tabular form. Adverse events will be tabulated by system organ class and preferred term after medical coding using the according to NCI CTCAE v 5.0.

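### Section 7.1.3 asks for regular urine-protein monitoring on cabozantinib, but the visit schedule sets no urine-protein test during treatment

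*Combined protocol and SAP*

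**What the plan says.** **Instruction.** Protocol 7.1.3, item 11: "Proteinuria was observed in 7% of patients receiving cabozantinib. Monitor urine protein regularly during cabozantinib treatment". The same item tells sites to stop cabozantinib if nephrotic syndrome develops. Section 7.1.2 includes nephrotic syndrome in the list headed "Permanently discontinue cabozantinib for any of the following".

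**Schedules.** In protocol Table 2 the urinalysis row has one mark at screening and one at the right-hand end. There is nothing under C1 to C6 or under C7 to progression. In the extracted text the second mark could belong to the end-of-treatment column or the one after it. The SAP 1.3.2 schedule puts it at end of treatment, with nothing under C1 to C4 or C5 to progression.

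**Visit texts.** The screening laboratory list in 8.2.1 names urinalysis: "TSH hormone levels, serology (HIV, HBV, and HCV), urianalysis and tumor markers". The on-treatment list in 8.2.2 ends without it: "hematological counts (total white blood cell count with leukocyte formula, haemoglobin, and platelet count), TSH hormone levels, and tumor markers". The end-of-treatment list in 8.2.3 also leaves it out: "TSH hormone levels, and tumor markers (NSE in tumors from cohort 1, CGA in tumors from cohort 5".

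**Extra tests.** Section 8.1 has assessments follow "this schedule of determinations and when clinically indicated according treating clinician (i.e: more frequent determinations in case of toxicities").

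**Reporting.** Protocol 10.7: "Vital signs, ECG parameters, clinical laboratory data (haematology, serum biochemistry, and urinalysis) will be presented in tabular form". SAP 1.5 repeats this.

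**The concern.** A site that works from Table 2 and the 8.2.2 list, as sites usually do, would never be prompted to test urine while the patient is taking cabozantinib. Several other 7.1.3 precautions do have a per-cycle slot, so this looks like an oversight rather than a decision.

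Two things are at stake. The first is surveillance. Proteinuria can be silent, and urine protein is the test that 7.1.3 names in the same item as the nephrotic-syndrome stopping rule. The second is reporting. Any post-baseline urinalysis table would combine end-of-treatment readings with readings taken because something prompted them, so it could not be read as a rate during treatment. The primary endpoint (ORR) and the two-stage rule are not affected.

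**Working it through.** The plan states no figure on this point, so there is none to reproduce. The check compares sections and then counts tests.

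**1. Instruction against schedule slot (7.1.3 against Table 2)**

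| 7.1.3 precaution | Slot during treatment |
|---|---|
| Blood pressure | Vital signs, every cycle |
| Liver function tests | Clinical chemistry, every cycle |
| Platelets | Haematology, every cycle |
| Electrolytes and biochemistry | Clinical chemistry, every cycle |
| Urine protein | None |

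**2. Number of scheduled tests.** Cycle *k* starts at week 3(*k* − 1). Time on treatment is not given in the documents, so three lengths are assumed. The last column counts a dipstick at every even-numbered cycle.

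| Assumed time on treatment | Cycles starting after C1 (chemistry panels) | Urine-protein tests as planned | Dipsticks if every second cycle |
|---|---|---|---|
| 3 months (13.0 weeks) | C2 to C5: 4 | 0 | C2, C4: 2 |
| 6 months (26.1 weeks) | C2 to C9: 8 | 0 | C2 to C8: 4 |
| 12 months (52.2 weeks) | C2 to C18: 17 | 0 | C2 to C18: 9 |

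The nominal gap between dipsticks would be 6 weeks.

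**3. Scale, under an assumption.** Section 7.1.3 gives 7% without dose or method. If that rate applied here, the expected number of patients with proteinuria would be 0.07 × 54 = 3.8 at the minimum sample size and 0.07 × 144 = 10.1 at the maximum. In a full cohort it would be 0.07 × 24 = 1.7.

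**4. How much could be missed.** Suppose onset is uniform over *T* weeks of treatment, an episode lasts *D* weeks, and the only test is at end of treatment. The chance of detection is then min(1, *D*/*T*). Both *D* and *T* are assumptions.

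| | *D* = 3 | *D* = 6 | *D* = 12 |
|---|---|---|---|
| *T* = 12 | 25% | 50% | 100% |
| *T* = 24 | 12.5% | 25% | 50% |
| *T* = 48 | 6.3% | 12.5% | 25% |

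A true 7% would therefore appear as anything from 7 × 0.0625 = 0.4% to 7 × 1 = 7%. Unscheduled testing under 7.1.3 or on clinical grounds would raise the lower figures by an unknown amount, possibly to the full 7%. The range is too wide to support any estimate of under-detection. It shows only that the answer depends on episode length, time on treatment and site practice, and the documents give none of the three.

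**The case against.** The case on the other side is substantial, and much of it stands.

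- **Section 7.1.3 is itself a protocol instruction and needs no trigger.** Investigators agree to follow the protocol, so a compliant site must monitor urine protein whatever Table 2 shows. This stands. What is missing is a frequency and a calendar slot.
- **Relevant checks are scheduled every cycle without a trigger:** creatinine, albumin, total protein, weight, vital signs and a targeted examination. The stopping rule concerns nephrotic syndrome, and albumin and weight bear on it directly. This also stands. None of these measures urine protein, however, so none covers a patient whose only sign is proteinuria.
- **Other routes exist.** The 8.1 clause allows extra tests, Appendix 1 asks for urine protein in a Grade 1 renal event, and 9.2.1.3 makes a management-changing abnormal value reportable. Each starts from a problem or result already recognised.
- **The 8.2.3 omission is editorial,** because that section refers back to 8.1 for what is required. Agreed.
- **The SAP schedule is weak corroboration.** It differs from the protocol in imaging window and cycle columns, and has no quality-of-life or tumour-marker rows. Agreed, but Table 2 and 8.2.2 carry the point without it.

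A reader might also infer a urine-specific reporting gap from the SAP having only baseline urinalysis shells (Table 19 and its cohort copies). The documents do not support that. The haematology and biochemistry shells (Tables 7 and 8) are baseline-only too, and all the shells under SAP 2.6 are AE, toxicity or SAE tables. That omission affects every laboratory domain.

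**Conclusion.** The point holds as an inconsistency between sections. The protocol requires regular urine-protein monitoring on cabozantinib, and its schedule and on-treatment laboratory list set no time for it. Testing in symptom-free patients would be inconsistent, and asymptomatic proteinuria could be missed or found late. It should be corrected because the toxicity is named, a permanent-stop rule is attached to nephrotic syndrome, and a slot is cheap to add.

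Three stronger readings go too far:

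- That kidney effects are unmonitored. The scheduled serum tests and the 7.1.3 instruction itself contradict this.
- That no urine is collected during treatment. A urine pregnancy test is permitted on treatment, so the gap concerns urinalysis and urine protein.
- That the trial will understate proteinuria by a known amount. The size cannot be determined. If proteinuria persists to the final test, or treatment is short, little would be lost.

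The test counts rest on 3-week cycles without delay and on the assumed treatment lengths. The case numbers rest on carrying the 7% over to this trial.

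**What to change.** 1. In Table 2, 8.2.2 and SAP 1.3.2, add a urine-protein dipstick at a stated interval, with quantification if positive. Day 1 of every second cycle would suit, because Table 2 already has quality-of-life visits at C2, C4, C6 and then "every 2 cycles (q6w, 42 days) thereafter until PD". Section 7.1.3 fixes no frequency, so the interval is a clinical choice.
2. List urinalysis in 8.2.3 so that it agrees with the schedule.
3. If treatment is too far advanced to add tests, state in the SAP that post-baseline urinalysis describes end-of-treatment or clinically triggered readings only. Give the number of patients assessed, and report no on-treatment proteinuria rate from it.

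**Cost.** Items 1 and 2 need a protocol amendment, with ethics review before implementation if substantial (12.2). Item 1 adds a few dipsticks per patient at visits already attended: 2, 4 or 9 over 3, 6 or 12 months. Section 5.7 expected the last enrolment in 3Q 2022, so the remaining treatment time decides whether items 1 and 2 are still worthwhile. Item 3 is a short addition to the SAP.
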